7.2 EEG measurements (4 month time points)

A sleep video/ EEG will be performed on babies recruited into the BabySMART study at approximately 4 months of age (conceptual). Parents will be invited to bring their child to the baby sleep lab, INFANT Research Centre in the CUH for this appointment. The timing of this should be coordinated so the recording commences following a feed around the time of the baby's longest daytime nap. The recording will last for the duration of the baby's sleep.

Recording parameters

The EEG recording will be made using the study EEG machine and follow the INFANT Sleep EEG Work Instructions which were devised according to the American Academy of Sleep Medicine (AASM) (10). Each recording will be made using disposable electrodes and will include respiration, Electrooculography (EOG), Electrocardiography (ECG) and Electromyography (EMG) measurements for qualification of sleep states.

EOG is a technique for measuring/ recording eye movements. Pairs of electrodes are typically placed either above and below the eye or to the left and right of the eye and the recorded potential is a measure of the eye's position.

ECG is the process of recording the electrical activity of the heart over a period of time using electrodes placed on the skin. These electrodes detect the tiny electrical changes on the skin that arise during each heartbeat from the heart muscle. These electrodes will be placed on the left and right deltoid muscle of the arm.

EMG is used to measure muscle movement and two electrodes will be applied approximately 2 cm to the left of the midline and 2cm to the right of the midline, with both electrodes approx. 2cm below the inferior edge of the mandible.

A specialized respiration electrode will be used to measure respiration rate. All recordings will be assigned a study ID number and pseudo anonymised. Any incident findings will be followed-up clinically.

BabySMART Protocol Version 2.0 20 JUL 2017

Protocol/Sponsor Number: GB02/17UCC Principal Investigator: [name]

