[name], Prof of Paediatrics and Consultant Neonatologist, Cork University Maternity Hospital [name], Senior Lecturer and Consultant Pediatrician, Department of Pediatrics and Child Health and INFANT, UCC Cork University Hospital

Protocol/Sponsor Number: GB02/17UCC Principal Investigator: [name]

1 Background

It is well known that sleep is essential for brain development (3) and learning (4). Infants require extensive sleep for development of the hippocampus, pons, brainstem, and midbrain and for optimizing physical growth. It is also essential for *brain plasticity*; the genetically determined ability of the infant brain to change its structure and function in response to the environment. Studies in young animals have shown that sleep deprivation leads to increased programmed cell death, smaller brain size, and loss of brain plasticity, all of which have negative long-term impact on behaviour and learning ability (5-7).

Infant massage, a form of systematic tactile stimulation by human hands, improves sleep hygiene. Very little is known about how massage influences early brain development but it is certainly linked to the theory of environmental enrichment, which has been well established in animal models. (8-10).

2 Aims of the BabySMART project

The aim of this project is to optimise the infant's sensory experience through a multi-sensory enrichment programme, including massage (a massage utilising a scented lotion before sleep each day), to encourage more structured sleep and ultimately show improved developmental and cognitive outcomes.

3 Hypothesis

The BabySMART study will examine the effect of a structured sensory enrichment programme including massage, delivered by parents according to a structured programme following training, on both the quality and quantity of sleep and on subsequent neurodevelopment

4 Significance of the question

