It is well known that sleep is essential for brain development and maturation. Studies have shown that sleep-deprived young animals have smaller brains with loss of brain plasticity, which leads to diminished learning and adverse long-term behavioural effects. It is also established that infant massage improves sleep hygiene and is linked to the theory of environmental enrichment, which promotes brain development. Brain development during the first years of life depends on the quality of stimulation in the infant's environment. Early child development is a life-long determinant of health and well-being. There are significant societal and economic benefits from optimal infant cognitive development (2).

Protocol/Sponsor Number: GB02/17UCC Principal Investigator: [name]

5 Trial Objectives and Purpose

Primary objective

To assess the effect of a structured sensory enrichment programme on Infant sleep using qualitative and quantitate measures.

Secondary objective

To assess the effect of a structured sensory enrichment programme on neuro-development as assessed by a standardised neurodevelopmental assessment at approx. 4 months and approx. 18 months of age.

6 Description of protocol methodology

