6.3 Contact with study participants

Mothers will be approached post- delivery, at the bedside, usually within 48 hours, in the wards in CUMH, they will be informed about the study and given a study leaflet to read. If they decide to participate in the study the consent form will be signed and the next steps will be explained to the parents.

BabySMART Protocol Version 2.0 20 JUL 2017

Protocol/Sponsor Number: GB02/17UCC Principal Investigator: [name]

Once the day of consent assessment is complete, ideally day 2 after birth, parents will be informed that the next appointment will be in approximately 2 - 3 weeks and that a member of the BabySMART team will contact them to schedule this appointment and randomisation will occur at this follow up visit.

Phone Call for follow on appointments in BabySMART

- 1. All postnatal appointments are to be made 1-2 weeks prior to scheduled follow-up.
- 2. Remind mothers of the BabySMART study; ask how baby has been getting on.
- 3. Schedule an appointment for follow up appointment in the INFANT research centre in the CUH (approx. 4 months and approx. 18 months).
- 4. Again, tell them we will send a reminder text the day before and if there are any problems to contact the study team and that an alternative appointment can be made.

Reminder texts

For the approx. 2 week, 4 month and 18 month visit texts

A reminder of your appointment with the BabySMART Study tomorrow in the INFANT Research Centre in CUH. Thanks from BabySMART

7 List of BabySMART Procedures

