7.1.1 Trans-epidermal water loss measurement (TEWL) (2 day, and 4 month time points)

Trans-epidermal water loss (TEWL) measurement will be taken using standard technique and equipment (Delfin Vapometer) at the visits occurring on approximately Day 2 and 4 months. Parents will be asked not to apply emollients on the morning of the visit and any non-compliance will be documented. Three measures will be taken and the average reading recorded in the eCRF.

BabySMART Protocol Version 2.0 20 JUL 2017 Page 7

Protocol/Sponsor Number: GB02/17UCC Principal Investigator: [name]

Page 8

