7.3 Sensory enrichment programme including infant massage

A total of 200 full term healthy infants will be recruited. Recruitment will take place at CUMH and UCL-ICH London. Parents will be invited to provide proxy consent for their infant to participate and also for their own participation in the BabySMART study.

Once Day 2 screening assessment is complete, parents will be informed that the next appointment will be in approximately 2 - 3 weeks and that a member of the BabySMART team will contact them to schedule this appointment. Randomisation will occur at this visit. Participants will be randomised to either a structured sensory enrichment programme including infant massage (intervention arm) or to the control arm.

The massage will be applied according to IAIM (International Association of Infant Massage). Created in 1976 by Vimala McClure, it is the first global organisation with a professional programme which is run in several countries around the world, due to its proven benefits. The purpose of IAIM is to create a nurturing touch and communication through training, education and research so that parents, caregivers and children are loved, valued and respected throughout the world community.

At the 2 week visit parents will be provided with training in infant massage by an instructor who has completed a Baby Massage Ireland trainer course. The massage should be carried out daily until the 4 month visit. Massage training will be completed on-site in the INFANT Research Centre in the new Paediatric unit in the CUH and the JOHNSON'S® HEAD-TO-TOE® extra moisturizing baby cream will be supplied at these appointments

Mothers will be informed about the enrichment programme which will include the benefits of baby massage, infant cues, duration of application, points of care for application and application technique at this stage. The technique of massage application will be shown to the mother by the researcher using a model baby (doll).

Mothers will be asked to apply the massage on their own baby as instructed and they will be observed to determine whether they applied the massage correctly or not. Training will be reinforced both at the training session and by the provision of a training DVD which will be provided to parents.

Baby massage education will also be given at drop in classes where a review of the strokes will be undertaken. Each parent's application of baby massage will be observed and evaluated for correct

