BabySMART Protocol Version 2.0 20 JUL 2017 Page 9

Protocol/Sponsor Number: GB02/17UCC Principal Investigator: [name]

technique. Extra JOHNSON'S® HEAD-TO-TOE® extra moisturizing baby cream will be supplied at these classes. Parents will be encouraged to massage their babies a minimum of 3 x 15-minute sessions including a minimum of 2 of the 6 areas to be massaged, every day for the first 4 months of life.

The researcher will follow HSE protocols to help women improve the care of their baby, or other questions that may arise; sleep positions, weaning, vaccines, feeding, bathing.

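### Does the missing rule on massage before the 4-month EEG nap undermine the EEG sleep comparison?

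*Combined protocol and SAP*

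**What the plan says.** - **Objective (section 5).** Sleep is the primary objective: "To assess the effect of a structured sensory enrichment programme on Infant sleep using qualitative and quantitate measures". No EEG variable is named as the primary endpoint.
- **Massage as a pre-sleep routine (section 2).** The aims mention, in a parenthesis, "a massage utilising a scented lotion before sleep each day".
- **Massage as delivered (section 7.3).** The working instruction does not mention sleep: "Parents will be encouraged to massage their babies a minimum of 3 x 15-minute sessions including a minimum of 2 of the 6 areas". On the end of the programme it says "The massage should be carried out daily until the 4 month visit". On the product it says "extra moisturizing baby cream will be supplied at these appointments".
- **EEG (section 7.2).** One sleep recording at about 4 months, lasting as long as the infant sleeps: "The timing of this should be coordinated so the recording commences following a feed", near the longest daytime nap. Massage is not mentioned. The recording is to follow the INFANT Sleep EEG Work Instructions, which are cited but not supplied.
- **Skin measurement (section 7.1.1).** Water loss through the skin is measured at about Day 2 and 4 months: "Parents will be asked not to apply emollients on the morning of the visit and any non-compliance will be documented".
- **Visit schedule (section 6.3).** "Schedule an appointment for follow up appointment in the INFANT research centre in the CUH (approx. 4 months and approx. 18 months". This suggests that the skin measurement and the EEG share one visit, but does not say so.
- **Adherence (section 7.5).** Parents record sleep and adherence to the programme in the app or in a paper diary, from birth to 4 months.

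**The concern.** The EEG is the only sleep measure in the readable text that parents do not report, and section 6.1 describes the trial as unblinded. Much of the weight of the sleep result may therefore rest on this recording. If massage acts on the sleep that comes straight after it, a massaged nap shows a lasting plus an immediate effect, and an unmassaged nap shows only the lasting one.

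Section 7.2 fixes the feed but not the massage. Section 7.1.1 appears to rule out massage with the supplied cream that morning, but not in the afternoon. The state of the recorded nap could then depend on the hour of the nap and on compliance with a rule written for a skin test. The EEG might also disagree with the diary simply because the diary describes sleep under the family's usual routine. The only visit-day departure that section 7.1.1 documents is emollient use.

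**Working it through.** **Step 1: read the sections side by side for the day of the visit.**

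| Section | What it implies for the recorded nap |
|---|---|
| 2 | Massage comes before sleep each day; stated only as an aim |
| 7.3 | Massage runs up to the 4-month visit; the visit day itself is not settled |
| 7.1.1 | No emollient that morning, hence no massage with the supplied cream that morning |
| 7.2 | Feed first, longest nap; silent on massage |

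Sections 7.3 and 7.1.1 pull in the same direction, towards a nap without cream massage. Section 7.1.1 therefore does not itself create a mixture. A mixture needs non-compliance (which is documented), massage without cream, or cream massage after the morning but before the recording. The readable text describes neither of the last two for the visit day.

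**Step 2: separate the cost of mixing from the benefit of massage.** The documents give 200 infants in total, with no effect size, standard deviation, alpha, power or allocation ratio. There is no planned figure to reproduce, so everything below is an illustration on assumptions: 1:1 allocation, 100 per arm, all recorded, two-sample t test, two-sided alpha 0.05, control SD 1.

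Let s be the lasting effect, a the immediate effect (both in SD units) and p the share of intervention infants massaged before the nap.

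- Expected difference: d = s + p·a
- Intervention-arm SD: √(1 + p(1 − p)a²)

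| s | a | Power at p = 0 | p = 0.5 | p = 1 |
|---|---|---|---|---|
| 0.2 | 0.2 | 29.1% (d = 0.20) | 55.8% (d = 0.30) | 80.4% (d = 0.40) |
| 0 | 0.4 | 5.0% (d = 0) | 28.6% (d = 0.20) | 80.4% (d = 0.40) |
| 0.3 | 0.2 | 56.0% (d = 0.30) | 80.2% (d = 0.40) | 94.0% (d = 0.50) |

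Across each row power rises because d rises. In every row the lowest power is at p = 0, which is a perfectly uniform condition. The rows show what a massage before the nap would add. They do not show what inconsistency costs.

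**Step 3: isolate the mixing.** Hold d fixed and compare a uniform arm (SD 1) with a mixed arm.

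- d = 0.30. Uniform (s = 0.3, p = 0): 56.0%. Mixed (s = 0.2, a = 0.2, p = 0.5): SD = √(1 + 0.25 × 0.04) = 1.005, power 55.8%. Loss: 0.2 points.
- d = 0.20. Uniform (s = 0.2, p = 0): 29.1%. Mixed (s = 0, a = 0.4, p = 0.5): SD = √(1 + 0.25 × 0.16) = 1.020, power 28.6%. Loss: 0.5 points.

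If a = 0, mixing has no effect at all.

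**Step 4: validity.** Whether a nap follows a massage is settled after randomisation and is part of how the assigned programme plays out. Comparing the arms as assigned remains unbiased for the effect of the programme as delivered. If the programme has neither a lasting nor an immediate effect, the false-positive rate is unaffected.

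**The case for a change.** The strongest reply is about meaning rather than power. If the EEG difference is positive, a reader may ask whether it reflects four months of enrichment or a massage an hour earlier. If it is null, a reader may ask whether the routine was simply withheld that day. The app or diary may show a visit-day session, but nothing in the readable text links it to the start of the EEG, so the question might be hard to answer afterwards. Stating the condition and recording the time of the last massage would cost very little.

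Part of this stands. Section 7.2 is silent, section 7.3 leaves the visit day open, and the pre-sleep wording of section 2 is not carried into the operative instruction. But the ambiguity matters only if there is an immediate effect and if a material share of infants are massaged before the nap, and the documents support a figure for neither. Section 6.1 frames the question as the effect of a programme over the first 4 months of life, which the comparison as assigned addresses. Section 7.2 also hands the conduct of the recording to work instructions, a natural home for pre-recording conditions. Asking the team to state a condition, without naming one that would give a better comparison, asks for detail and does not improve the method. A sentence and a time field would be a harmless courtesy, with the choice of condition left to the investigators.

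**Conclusion.** The observation is accurate, but it is a gap in operational detail that the study team can fill sensibly, and the plan need not change. The readable text leans towards a recorded nap without cream massage, the emollient request does not cause mixing, and the randomised comparison is valid either way. In the two matched comparisons, mixing costs 0.2 and 0.5 percentage points of power. Those figures rest on assumed effects of 0.2 to 0.4 SD, half the intervention infants massaged before the nap, and 100 recorded infants per arm.

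The residual point is whether an EEG difference should be described as lasting or as lasting plus immediate. An analyst can handle it when interpreting the result, using the documented emollient non-compliance and whatever the adherence records show for that day. The conclusion also assumes that the skin measurement and the EEG fall on the same day, and it makes no claim about Figure 1 or the EEG work instructions, neither of which is available.

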7.3 Sensory enrichment programme including infant massage

A total of 200 full term healthy infants will be recruited. Recruitment will take place at CUMH and UCL-ICH London. Parents will be invited to provide proxy consent for their infant to participate and also for their own participation in the BabySMART study.

Once Day 2 screening assessment is complete, parents will be informed that the next appointment will be in approximately 2 - 3 weeks and that a member of the BabySMART team will contact them to schedule this appointment. Randomisation will occur at this visit. Participants will be randomised to either a structured sensory enrichment programme including infant massage (intervention arm) or to the control arm.

The massage will be applied according to IAIM (International Association of Infant Massage). Created in 1976 by Vimala McClure, it is the first global organisation with a professional programme which is run in several countries around the world, due to its proven benefits. The purpose of IAIM is to create a nurturing touch and communication through training, education and research so that parents, caregivers and children are loved, valued and respected throughout the world community.

At the 2 week visit parents will be provided with training in infant massage by an instructor who has completed a Baby Massage Ireland trainer course. The massage should be carried out daily until the 4 month visit. Massage training will be completed on-site in the INFANT Research Centre in the new Paediatric unit in the CUH and the JOHNSON'S® HEAD-TO-TOE® extra moisturizing baby cream will be supplied at these appointments

Mothers will be informed about the enrichment programme which will include the benefits of baby massage, infant cues, duration of application, points of care for application and application technique at this stage. The technique of massage application will be shown to the mother by the researcher using a model baby (doll).

Mothers will be asked to apply the massage on their own baby as instructed and they will be observed to determine whether they applied the massage correctly or not. Training will be reinforced both at the training session and by the provision of a training DVD which will be provided to parents.

Baby massage education will also be given at drop in classes where a review of the strokes will be undertaken. Each parent's application of baby massage will be observed and evaluated for correct

BabySMART Protocol Version 2.0 20 JUL 2017 Page 9

Protocol/Sponsor Number: GB02/17UCC Principal Investigator: [name]

technique. Extra JOHNSON'S® HEAD-TO-TOE® extra moisturizing baby cream will be supplied at these classes. Parents will be encouraged to massage their babies a minimum of 3 x 15-minute sessions including a minimum of 2 of the 6 areas to be massaged, every day for the first 4 months of life.

The researcher will follow HSE protocols to help women improve the care of their baby, or other questions that may arise; sleep positions, weaning, vaccines, feeding, bathing.

7.1.5 Neurodevelopment assessments (4 month and 18 month time points approximately)

All participants in the study will receive a standardised developmental assessment at 4 months and 18 months of age approximately. The Griffiths III Mental Development Scales published in 2016, measures development trends which are significant for intelligence, or indicative of functional mental growth in babies and young children. The new Griffiths III measures maturation from 0 to 5 years 11 months of age. Griffiths III is a restricted test that is available only to the holders of an ARICD Certificate of Registration as User. Griffiths training courses are open to paediatricians and psychologists.

Allied Health Professionals who are

- 1) part of a Child Development Team, or
- 2) actively involved in research or monitoring, and
- 3) can be supervised by an experienced Griffiths user, may also apply.

Neurodevelopment assessment using the Griffiths III will be performed by a trained member of the INFANT team and will be conducted using the recognised Griffiths kit, manual, and other related material. Assessments will take place in the Early Life Lab, INFANT Discovery Platform in CUH or if required the INFANT researcher will travel to the infant's home.

The new Griffiths III provides an overall measure of a child's development, as well as an individual profile of strengths and needs across five areas:

A: Foundations of Learning

B: Language and Communication

C: Eye and Hand Coordination

D: Personal - Social - Emotional

E: Gross Motor

Any worrying or incidental findings will be referred for follow up along the relevant clinical pathway.

BabySMART Protocol Version 2.0 20 JUL 2017 Page 10

Protocol/Sponsor Number: GB02/17UCC Principal Investigator: [name]

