6.1 Type of Trial

We will undertake a multi-centre, unblinded, randomised, controlled study to evaluate whether a multi-sensory enrichment programme in the first 4 months of life will improve sleep architecture and neurodevelopment in healthy infants.

We do not interpret this study as a clinical trial, as defined by the Control of Clinical Trials Act, 1987 and 1990.

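### Section 6.1 calls the study unblinded without distinguishing roles, and the available text does not require the Griffiths III examiner or the EEG sleep scorer to be masked, though both could be for most families

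*Combined protocol and SAP*

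**What the plan says.** Section 6.1 describes the design in one sentence: "We will undertake a multi-centre, unblinded, randomised, controlled study". The label appears without any breakdown by parent, instructor, examiner, scorer or analyst.

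For the Griffiths III at about 4 and 18 months, section 7.1.5 covers training, kit, manual and venue. On access to the test it says: "Griffiths III is a restricted test that is available only to the holders of an ARICD Certificate of Registration as User". On who carries it out: "Neurodevelopment assessment using the Griffiths III will be performed by a trained member of the INFANT team". On venue, the default is INFANT premises in the hospital, but "if required the INFANT researcher will travel to the infant's home".

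For the sleep video/EEG at about 4 months, section 7.2 says: "All recordings will be assigned a study ID number and pseudo anonymised". It refers the recording method to separate INFANT work instructions based on the AASM scoring manual. It does not say who stages the sleep.

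For the intervention, section 7.3 says "parents will be provided with training in infant massage by an instructor who has completed a Baby Massage Ireland trainer course". The same section has a researcher, not further identified, demonstrate the strokes on a doll. Training takes place at the INFANT Research Centre.

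Section 7.5 has parents enter adherence to the programme, and its acceptance, in the app. Access is limited to the study's research staff. The app is optional, with a paper diary as the alternative. The 4- and 18-month questionnaires in the Appendix ask about attending a massage course, using massage in the daily routine, and the product used.

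**The concern.** An open design is unavoidable for the people who give or teach massage. It does not follow that the people who measure outcomes must know the arm. The Griffiths III is administered in person by a team member, and sleep staging involves a human reading of the trace. In both, knowledge of allocation can shift borderline judgements in one direction, and a larger sample does not remove such a shift.

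Under section 5, sleep is the primary objective and neurodevelopment at the two ages is the secondary one. A study run exactly to the text could use raters who know the arm for both the EEG part of the first and the whole of the second. A difference between arms would then be open to the criticism that the assessors produced it, and the protocol would offer no answer.

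**Working it through.** The plan gives no figure on this point, so the check is a reading of the sections side by side.

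**Step 1: who could be masked, and what is required.**

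| Role | Could be masked? | Requirement in the available text |
|---|---|---|
| Parent | No: delivers the massage | None possible |
| Massage instructor | No: teaches it | None possible |
| Griffiths III examiner | Yes, if not involved in that family's training | Trained and registered; nothing on allocation (7.1.5) |
| EEG sleep scorer | Yes: works from coded files | Files coded; no scorer named, nothing on allocation (7.2) |

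The feasibility column is my inference. Coding the files makes masked staging possible but does not require it, since a scorer could hold both the ID and the allocation.

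**Step 2: how a rater could learn the arm.** These are possibilities that the text leaves open, not stated plans.

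- *Overlapping roles.* The instructor needs a massage trainer course and the examiner a Griffiths registration, so overlap is less likely. But 7.3 and 7.1.5 both use the generic word researcher, and no rule keeps the roles apart for a given family.
- *Adherence data.* Section 7.5 does not say whether the examiner or scorer is among the staff with access.
- *Questionnaires.* The text does not say whether the examiner sees the massage items. A control family might also use massage, so the answers would suggest the arm without proving it.

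**Step 3: what can be repaired afterwards.** Coded EEG files can be staged, or re-staged, by a masked scorer. Section 7.1.5 mentions no recording of the Griffiths session, so masked re-scoring may not be possible. Later assessments can still be protected: the two Griffiths time points lie about 18 − 4 = 14 months apart, and section 12 provides an amendment route.

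**Step 4: illustration only.** The documents give no bias size. Assume 1:1 allocation, one two-sided 5% t-test, no true effect, and a constant scoring shift of *d* SD in favour of massage. The rejection probability comes from the noncentral t distribution with 2*n* − 2 degrees of freedom and noncentrality *d*√(*n*/2), with *n* per arm. Only the total of 200 is from the protocol (200/2 = 100 per arm); 80 per arm assumes 20% loss.

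| Assumed shift *d* | 100 per arm: noncentrality, false-positive rate | 80 per arm: noncentrality, false-positive rate |
|---|---|---|
| 0 | 0, 5.0% | 0, 5.0% |
| 0.05 | 0.354, 6.4% | 0.316, 6.1% |
| 0.1 | 0.707, 10.8% | 0.632, 9.6% |
| 0.2 | 1.414, 29.1% | 1.265, 24.2% |

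The rate doubles to 10% at a shift of 0.093 SD (100 per arm) or 0.104 SD (80 per arm). Section 7.1.5 describes an overall measure and five areas at two ages, and no test is specified, so a single t-test is a simplification. The conclusion does not rest on this table.

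**The case against.** The strongest reply is that silence is not a plan to use unmasked raters. Section 6.1 uses the word once and lists no roles. The work instructions that govern the EEG are a separate document, and the flow chart (Figure 1) is not visible, so either might contain a masking rule. The massage and Griffiths qualifications differ, every route in step 2 is conjecture, and the number of registered examiners is not given, so full separation may not be practicable.

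Much of this stands, and it limits the point. A reader might infer that the protocol declares every role unblinded; it only fails to distinguish them. A reader might infer that the examiner also teaches massage; generic job words do not show that. A reader might infer that a Griffiths assessment can never be re-scored because it is scored on the spot; the text does not say how or when it is scored, and is merely silent about recording. Nor do two recruiting sites and home visits show that separation must fail for some families, only that it may. On the EEG side, the absence of a rule is established only for the text at hand.

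What the reply does not remove is that section 7.1.5 is the place where an examiner rule belongs. It gives detailed conditions for that role and includes none on allocation.

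**Conclusion.** The point holds in a limited form. Section 6.1 does not distinguish roles, and no available text requires the Griffiths III examiner or the EEG sleep scorer to be unaware of allocation or separate from massage training and adherence data. The plan thus permits avoidable observer bias in the secondary outcome and in EEG sleep staging.

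It does not show that bias occurred or would occur. A reader might take the illustrative false-positive rates as an estimate of harm; the documents support no such reading, because every shift is assumed and the true one may be zero.

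Placing the Griffiths ahead of the EEG is a judgement. It rests on recoverability and not on the rank of the objective, since sleep is primary. Parent-recorded sleep cannot be masked and lies outside this point. The change should be made, with medium confidence. The conclusion assumes that neither the EEG work instructions nor Figure 1 already contains a masking rule, and that enough registered users exist to separate roles for most families.

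**What to change.** Suggested wording:

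- **6.1:** *Parents and massage instructors are not masked; the EEG sleep scorer is masked to allocation, and the Griffiths III examiner is masked wherever possible, with exceptions logged.*
- **7.1.5:** *Using existing registered users, the examiner is one who did not train, observe or run massage classes for that family and has no access to allocation. Parents are asked not to mention massage. Any unmasking, and any family for whom separation was not possible, is logged.*
- **7.2:** *Sleep is staged from ID-coded files by a scorer without access to allocation.* If the EEG work instructions already say this, a citation is enough.
- **7.5 and questionnaires:** *Adherence entries (app or diary) and massage items are withheld from the examiner until testing is done, and from the scorer.* This must leave the follow-up of the depression questionnaire described in 7.4.3 unchanged.

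For the scorer and the app or diary data, the cost is an access rule on files that are already coded. For the Griffiths, it is tighter scheduling among registered staff whose number is not given, and visit order must still fit the nap-timed EEG. Some accidental unmasking will have to be logged. If the study is running, section 12 requires an ethics-approved amendment; masked re-staging can still cover EEG files already recorded, but the examiner rule protects only assessments still to come. If masking is already practised, writing it down costs little and lets readers credit it.
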